An unpublished clinical trial conducted in India of Shoden® (CTRI/2020/10/028397) evaluated the PK of three withanolides (withanolide A, withaferin A, and withanoside IV) in 16 healthy adults, aged 18-45 years. All three withanolides were detected by LC-MRM-MS in plasma (data provided by Arjuna LTD under a NDA).⁷⁹ This study was limited in scope due to the dose (480 mg), which was higher than that used in clinical trials involving Shoden®,^{52,53,57} the lack of older participants, and the limited range of withanolides targeted.

E.3. LC-MS detection of withanolides

As part of ongoing research at the BENFRA Center, [name] and the BSR/PKCore at OHSU have been developing LC-MS methods of detecting withanolides in mouse plasma, which will be optimized for human plasma and urine as part of the study. Figure 2 demonstrates good separation for several of the withanolides that will be analyzed in this study.

F. RESEARCH DESIGN AND METHODS

F.1. Study design

The proposed study is a randomized, double-blind, crossover trial evaluating (a) the PK of withanolides, from two doses of a commercially available WS root and leaf extract (Shoden®), (b) safety and tolerability of these doses and (c) the feasibility of remotely measuring sleep- and stress-related outcomes in older adults. Participants will be randomized to one of two dose sequence groups. There will be two 4-week study periods separated by a 2- to 4-week washout period. During each study period, participants will attend a 13-hour baseline PK study visit and return for 24- and 48-hour blood and urine collections. After the 48-hour visit, they will continue taking Shoden® at the administered dose (240 or 480 mg) for four weeks, at which time they will return for a follow-up visit. A flow chart of the study is provided in Figure 3.

Study Design Diagram

[figure not shown]

Figure 3. Study design. *Mini Mental State Examination (MMSE); #Geriatric Depression Scale (GDS); *Biometrics: weight, height, body mass index (BMI), age, blood pressure, pulse rate, temperature; *Lab measures: complete blood count (CBC), comprehensive metabolic panel (CMP), urinalysis, and TSH; * REDCap surveys delivered to and completed by participants in the week prior to each PK visit and 4-Week Follow-Up Visit. §Safety assessment at study visits includes safety labs (CBC, CMP, TSH, testosterone, UA), GDS-15, ECG, and AE questionnaire.

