Randomization and blinding will be done by the OHSU research pharmacy. A single dose of Shoden® will be dispensed by the research pharmacy to a member of the study team just prior to the participant's baseline PK visit for each study period. Participants will receive two single administration doses of Shoden® (240 and 480 mg). The order in which they receive these doses will be random to prevent a tolerance effect. The OHSU Research Pharmacy will randomize participants to one of two dose sequence groups, stratified by sex. Participants will consume Shoden® in the presence of a study team member following baseline measurements in order to ensure adherence to the study protocol. Prior to the 48-hour visit for each study period, a 35-day supply of Shoden® (240 or 480 mg per day) will be dispensed to a study team member. Whenever the study intervention is dispensed, the OHSU research pharmacy will record the date, participant ID number, and dose for accountability.

H.2. Administration

A single dose (240 or 480 mg) of the study intervention will be administered in an outpatient setting at each baseline PK visit. The dose sequence will be randomized. The research pharmacy will dispense one dose of Shoden® to a member of the study team, who will provide it to the participant for oral consumption. At the 48-hour visit for each study period, participants will be given a 35-day supply of the study intervention.

H.3. Criteria for intervention discontinuation and stopping guidelines

Participants will be advised during the informed consent process that they have the right to permanently discontinue Shoden® and/or withdraw from the study at any time without negative repercussions. Participants will also be counseled during the consent process that they may be withdrawn from the study at the discretion of the Principal Investigator or designees. A participant may discontinue and/or withdraw and/or be withdrawn from the study for the following reasons:

Administrative:

- 1) Withdrawal of participant consent
- 2) Request of site investigator or designees
- 3) Request of primary care physician
- 4) Non-compliance
- 5) Protocol deviation
- 6) Premature termination of the study

Adverse event (AE)/experience:

- 1) Worsening of pre-existing disease
- 2) Intercurrent illness
- 3) Death
- 4) Major/clinically significant alteration in laboratory values or biometric assessments after beginning product

- 5) Other AE

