1.4.1. Baseline Visit (0-12hr)

Visit Timing: For the first study period, Baseline Visit 1 will occur a minimum of three days after the screening visit to allow for review of laboratory results and scheduling of appropriate facilities. For the second study period, Baseline Visit 2 will occur a minimum of two weeks (and not more than three weeks) after the four-week follow-up visit for the first study period.

Sample collection: Participants will be asked to fast for 10-12 hours, excluding water, the night before each baseline visit in an attempt to standardize gastrointestinal transit time and minimize delayed absorption of the study intervention due to the presence of food. Participants will be reminded during the pre-visit reminder call to arrive at the visit well-hydrated to facilitate blood collections. Study staff will place a peripheral intravenous catheter in the participant's arm or hand to allow for serial plasma specimen collection. Prior to administration of Shoden®, a baseline plasma sample of two teaspoons (10 ml) will be collected through the catheter using a syringe and transferred immediately into a heparinized Vacutainer tube. The participant will then be administered two capsules of Shoden® (240 or 480 mg total) on an empty stomach in the presence of study staff to ensure compliance. Participants will be asked to abstain from food and drink (excluding water) for the first two hours following consumption of Shoden® capsules to allow for transition into the small intestine and absorption. If signs of hypoglycemia are present, participants will be allowed to consume a high glycemic food and monitored for improvement. Participants will be provided water at the visit and will be encouraged to drink four 16-ounce cups of water over the 12 hours to maintain good hydration status. Serial blood samples (two teaspoons (10 ml) per sample) will be collected through a peripheral intravenous catheter, at 15, 30, 45, 60, 90, 120, 150, 180, 210, 240, 300, 360, 540, and 720 minutes after dosing. A baseline urine sample and a 12-hour pooled urine collection will be obtained to measure excretion of WS metabolites.

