Tolerability and safety: Participants' weight, height, body mass index, age, blood pressure, temperature, respiration rate, and pulse rate will be recorded at each study visit to monitor for adverse events and asymptomatic illnesses that may impact study results. Vitals will be collected at baseline, 7 hours post-Shoden administration, and at the end of each baseline visit. At the beginning of each baseline visit, participants will complete an electrocardiogram (ECG) and the Geriatric Depression Scale-15. Four teaspoons of blood (20 ml) will be collected for safety labs (CBC, CMP, urinalysis, TSH, serum total testosterone). ECG will be repeated 7 hours post-intervention to assess for cardiac changes. One teaspoon (5 ml) will be collected for a repeat CMP at 10 hours post-intervention to evaluate kidney and liver function. Participants will be interviewed and administered a standardized multi-system adverse events questionnaire at the beginning and end of each baseline visit. This visit is expected to take 13 hours a total of 175 mL of blood will be collected.

If the baseline CBC shows hemoglobin or hematocrit levels below what is recommended by the FDA for blood donation, the visit will be halted immediately. Participants will be asked to stay for 2.5 hours after the study agent has been administered to assess for acute side effects. Two and a half hours was chosen because common withanolides have reached their C_{MAX} by this time based on a previous PK study using Shoden®.⁸⁰ The end-of-visit adverse events questionnaire will be administered by phone and missed safety evaluations (7-hour ECG and vitals, 10-hour CMP, 12-hour vitals) will be collected at the 24-hour visit. After the 24-hour visit, the participant will be withdrawn from the study.

If study staff have difficulties collecting blood samples for any reason, the decision may be made to halt the visit. Participants will be asked to stay for 2.5 hours after the study agent has been administered to assess for acute side effects. If the visit ends before the 7-hour mark, the end-of-visit adverse events questionnaire will be administered by phone and missed safety evaluations (7-hour ECG and vitals, 10-hour CMP, 12-hour vitals) will be collected at the 24-hour visit. Participants will be allowed to remain on the study if difficulties with blood sample collection were the only reason for halting the study visit early.

I.4.2 24- and 48-Hour Visits

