Participants will return at 24 hours and 48 hours for a single blood collection (two teaspoons (10 ml)) and urine collection. Vitals will be collected. A CMP and ECG may be collected at the 24-hour visit if the baseline visit was halted prior to 7 hours. At the 48-hour visit, the adverse events questionnaire will be administered as the baseline measure for the subsequent four-week period. After the 48-hour visit, participants will be issued a 35-day supply of the appropriate dose of Shoden® (240 or 480 mg), which they will begin taking before bed every day for four weeks. These visits are expected to take 20 minutes. After analyzing the plasma and urine samples for the first two participants, a determination will be made as to whether the 48-hour PK visit is needed for future participants. If no withanolides are detected in plasma or urine at 48-hours, this time point will be eliminated to avoid undue participant burden.

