a 15-minute LC-MRM-MS method for the BENFRA Center for the analysis of seven withanolides using digoxin-d₃ as an internal standard (section E.3, Figure 2). The BENFRA center (through [name]) is working with the BSR/PKCore lab to include the four additional withanolides in the method and optimize mouse plasma work-up methods for the analysis. These methods will be adapted for human plasma and urine in this study, using commercially available human plasma and urine spiked with reference withanolides under the guidance of [name] and [name], director of the BSR/PKCore.

Each withanolide analyte will be identified by its retention time and characteristic mass spectral fragmentation pattern using selected reactions within a multiple-reaction monitoring paradigm. The peak area ratio to the appropriate internal standard will be identified and evaluated against the standard calibration curve of each analyte prepared by spiking known concentrations into blank plasma. Each analyte's concentration in participant plasma will be used to generate a concentration-time curve for pharmacokinetic profiling. The primary endpoints are the maximum concentration (C_{max}) and its corresponding timepoint (t_{max}) of each withanolide analyte. To determine the rate of elimination (k), linear regression of the plasma concentration against time will be used. This value will be used to determine the elimination half-life ($t_{1/2}$) using the formula $t_{1/2}=0.693/k$. Area under the concentration-time curve from dosing (time 0) to time t (AUC_{0-t}) will be calculated using the linear-log trapezoidal method. Area under the concentration-time curve from dosing (time 0) extrapolated to infinite time ($AUC_{0-\infty}$) will be calculated using the equation $AUC_{0-t} + AUC_{t-\infty}$, where $AUC_{t-\infty} = C_{last}/k_e$. C_{last} is the last observed concentration and k_e is the elimination rate constant. Differences in C_{max} , AUC_{0-t} , $AUC_{0-\infty}$, and $t_{1/2}$ for the two doses of Shoden® will be evaluated using paired t-tests or the non-parametric equivalent Wilcoxon paired test, while differences in t_{max} will be compared between dose groups using chi-square tests of distribution. With numerous analytes of interest, post-hoc multiple comparison adjustments in p-values will be applied using the Holm-Sidak stepwise correction. All final statistical tests will be two-tailed and considered significant at $\alpha=0.05$.

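### L.1 compares t_max, a primary endpoint, with a chi-square test that ignores the crossover pairing and the order of the sampling times, so modest shifts in time to peak are likely to be missed

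*Combined protocol and SAP*

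**What the plan says.** A.3 lists T_max among the primary endpoints, and L.1 repeats this: "The primary endpoints are the maximum concentration (C_{max}) and its corresponding timepoint (t_{max}) of each withanolide analyte".

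F.1 sets the design: "The proposed study is a randomized, double-blind, crossover trial". Under H.1 each participant takes a single 240 mg dose and a single 480 mg dose, in random order.

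For C_max, both AUCs and half-life, L.1 says that dose differences "will be evaluated using paired t-tests or the non-parametric equivalent Wilcoxon paired test". The same sentence then says that t_max "will be compared between dose groups using chi-square tests of distribution". It gives no categories for t_max, no paired or exact version of the test, and no effect estimate. Holm-Sidak adjustment is to be applied because there are many analytes, and tests are two-sided at 0.05.

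Blood is drawn in the first 12 hours "at 15, 30, 45, 60, 90, 120, 150, 180, 210, 240, 300, 360, 540, and 720 minutes after dosing" (I.4.1), and under I.4.2 "Participants will return at 24 hours and 48 hours for a single blood collection". L.4 bases the sample size on 10 completers and a paired t-test, illustrated on C_max.

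**The concern.** Ten completers give ten pairs of t_max values per analyte. A chi-square test of two dose groups against time treats them as 20 unrelated observations. That raises three problems.

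- **Pairing.** Two values from one person are not independent. The test throws away the within-person comparison that the crossover was designed to provide.
- **Order.** The statistic treats 90, 120 and 540 minutes as unordered labels, so it cannot tell a small delay from a large one.
- **Sparseness.** The chi-square approximation relies on adequate expected counts, which 20 values spread over many sampling times cannot supply.

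A.1 says that the data will inform dosage and dosing frequency in later trials. A non-significant result could be taken as evidence that time to peak does not depend on dose, when the test had little chance of showing a modest difference.

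**Working it through.** **The plan's own power figure.** L.4 gives 95% power for a paired t-test with n = 10 and d = 1.3. The noncentral t with 9 degrees of freedom and noncentrality 1.3 × √10 = 4.11 gives 95.4% two-sided, so the figure reproduces. It applies to a paired t-test and says nothing about the chi-square test of t_max.

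**Cell counts.** There are 14 post-dose times to 12 h plus 24 h and 48 h, so at most 16 possible values. I.4.1 expects common withanolides to have peaked by 2.5 h, which leaves 7 nominal times (15, 30, 45, 60, 90, 120 and 150 min). With 7 occupied times the average expected count is 20 / (2 × 7) = 1.4; with more it is lower.

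**Worked cases that need no variability assumption** (each sampling time its own category):

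1. Put two participants at each of five successive times at one dose, and move every one of them one sampling time later at the other. Only the first and last columns differ (2 v 0 and 0 v 2, expected 1 per cell). Each adds 2, so chi-square = 4 on 5 df and p = 0.55. In the signed-rank test all ten differences have the same sign, so exact p = 2 / 2^10 = 0.002.
2. Move everyone two sampling times later. Four columns differ, so chi-square = 8 on 6 df and p = 0.24. Signed-rank p is again 0.002.
3. Start from five participants at 60 min and five at 90 min. At the other dose put five at 90 min and five at 120 min, or five at 90 min and five at 540 min. Either way chi-square = 10 on 2 df and p = 0.0067. The size of the delay does not enter.
4. Let the two doses share no t_max value at all. Chi-square takes its maximum, 20, on k − 1 df for k occupied times. With k = 13, p = 0.067, so 0.05 is out of reach. The first Holm-Sidak step for 11 analytes is 1 − 0.95^(1/11) = 0.00465. With k = 8, p = 0.0056 misses it; with k = 7, p = 0.0028 passes.

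**Simulation.** The documents give no t_max variability, so these inputs are assumed: log-normal t_max, median 1.5 h, values placed on the protocol's sampling times, 10 pairs, unadjusted alpha 0.05, each sampling time its own category.

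| Log SD between / within | Delay | Chi-square | Exact signed-rank |
|---|---|---|---|
| 0.3 / 0.2 | 1.5-fold | 10–11% | 90–91% |
| 0.3 / 0.2 | 2-fold | 38–41% | about 100% |
| 0.5 / 0.25 | 1.5-fold | 3–4% | 76–79% |

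The ranges are spreads over repeated runs.

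A wider set of assumptions (median 60 to 150 min, CV 30 to 50%, within-person correlation 0 to 0.8) gives:

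| Shift | Chi-square, 0.05 | Signed-rank, 0.05 | Chi-square, 0.00465 | Signed-rank, 0.00465 |
|---|---|---|---|---|
| 1.5-fold | 3–31% | 34–99.5% | 0–4% | 4–72% |
| 2-fold | 14–77% | 77–100% | 0.1–14% | 27–100% |
| 3-fold | 47–98% | 99–100% | 0.3–18% | 74–100% |

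With no true shift, chi-square rejected in 0.4 to 2.6% of runs at nominal 5%.

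**The case against.** **L.1 does not call the test unpaired and does not define categories.** Both points are fair. An unpaired test is still the natural reading of a comparison between dose groups placed beside tests that are explicitly paired. The categories matter more. With median 1.5 h and SDs 0.3/0.2, a fixed split at 2 h raises chi-square power to about 36% for a 1.5-fold delay and 91% for a 2-fold delay. Three bins (up to 1 h, 1 to 2 h, over 2 h) give 36% and 89%. With SDs 0.5/0.25, the 2 h split gives 13% and 50%. Binning therefore recovers much of the loss for large shifts, but at 1.5-fold it remains far behind the paired test.

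**The assumed delays may not occur.** This also stands. The Aim 1 hypothesis concerns detectability and higher plasma levels at 480 mg; it predicts nothing about t_max. The estimates of t_max themselves are unaffected, this is a 12-person pilot, and the data would still allow a paired analysis later.

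**Stronger readings that the documents do not support.**

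- A reader might infer that the test has almost no power. That fits modest shifts with wide spread, or most scenarios after Holm-Sidak. It does not fit large shifts: unadjusted power reaches 77% at 2-fold and 98% at 3-fold.
- A reader might infer that violating independence inflates false positives. In the simulations the test is conservative.
- A reader might infer that the two study periods are being treated as independent groups. L.1 compares doses, and because sequence is randomized, dose and period are not the same thing.

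**The signed-rank test is not a complete answer.** It does not adjust for period, but neither do the paired tests already in L.1. Its power also falls after Holm-Sidak, and L.1 does not define the family. If that were 11 analytes × 5 parameters = 55 tests, the first step would be 1 − 0.95^(1/55) = 0.00093. That is below the smallest p that the signed-rank test can give with 10 pairs (0.00195).

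**Conclusion.** The point holds in a limited form. The chi-square test does not fit paired, ordered t_max data, and no other section corrects it. The consequence is a conservative test with far less power than a paired one for modest shifts: about 10% against 91% for a 1.5-fold delay and 38 to 41% against about 100% for a 2-fold delay, under the first set of assumptions in the working.

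Those power figures depend on assumed variability and delay, on one category per sampling time and on unadjusted alpha. The mismatch with the design does not depend on them, nor do the worked cases on any variability assumption. A non-significant chi-square result would say little about whether time to peak differs by dose. Because false positives are not inflated, t_max estimation is untouched and the study is a pilot, this is something that should be fixed and not a fatal flaw.

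**What to change.** In L.1, delete the chi-square test for t_max. Replace it with the Wilcoxon signed-rank test on within-participant differences in t_max (480 mg minus 240 mg) for each analyte, and report the median paired difference with a Hodges-Lehmann confidence interval. The interval lets a reader see which delays the data exclude, whatever the p-value.

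In the same edit, state which tests form the Holm-Sidak family, since this decides whether 10 pairs can reach significance at all.

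The cost is one sentence for the test and a clause for the family. L.1 already names the Wilcoxon paired test for the other parameters, and no new data, visits or participants are needed.

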Study Title: Safety, tolerability, and pharmacokinetics of an oral *Withania somnifera* product in older adults

Principal Investigator: [name], ND, MS

IRB#: STUDY00026055

Version Date: 10.10.2024

F.2. Study Population

F.2.1. Number of participants

Twelve non-demented older volunteers (6 female, 6 male) 65 years of age or older will be screened and enrolled in the study. We estimate that we will need to screen approximately twenty potential participants to meet the twelve volunteers needed to complete the study. We expect two dropouts, for a total of 10 participants completing the study.

F.2.2. Inclusion and exclusion criteria

Inclusion criteria:

1. Age 65 and older, male and female
2. Body Mass Index (BMI) greater than 17 and less than 35 at screening
3. Sufficient vision and hearing to complete all tests
4. Willingness to discontinue all botanical supplementation for one week prior to and throughout study
5. No known sensitivity to *Withania somnifera* or any of its derivatives
6. Normal or clinically not significant 12-lead electrocardiogram (ECG) recording
7. Hepatic (ALT, AST, bilirubin), renal (creatinine, estimated GFR), and TSH parameters within normal range
8. Hemoglobin ≥ 13.0 g/dL or hematocrit $\geq 39\%$ (males) OR hemoglobin ≥ 12.5 g/dL or hematocrit $\geq 38\%$ (females), per FDA recommendations on blood donation
9. General health status that will not interfere with the ability to complete the study
10. Willingness to attend all study visits
11. Willingness to avoid caffeine and xanthine-containing foods or beverages (e.g., coffee, tea, chocolate, caffeine-containing sodas, colas, etc.), as well as grapefruit juice and poppy-containing foods for 48 hours prior to baseline visits
12. Willingness to adhere to special diet (no dairy, grapefruit products, poppy-containing foods, high-fat meals, caffeine, or xanthine-containing foods or beverages) during baseline visits and until after 24-hour visit
13. Mini-Mental State Exam (MMSE) score ≥ 27

Exclusion criteria:

1. Current smoking, alcohol, or substance abuse according to DSM-V criteria
2. Participants who are currently pregnant, actively trying to conceive a child, or planning to within three months of study completion
3. Severe aversion to venipuncture
4. Donation of blood within 90 days of screening
5. Participation in drug research study within 90 days of screening

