Peak area for each withanolide analyte and internal standard will be obtained using Analyst software from Sciex Technologies (version 1.7.1). The Core lab will provide and set up LC-MRM-MS instrumentation. The applicant will prepare the plasma and urine samples for analysis in [name] lab and retrieve and analyze the LC-MRM-MS data generated at the Core Lab to obtain concentrations of each withanolide in each sample. The applicant will work with [name] to obtain PK curves and parameters.

L.2. Safety analysis (Aim 2)

Changes in laboratory outcomes from the baseline visit to the four-week follow-up visit for each study period will be presented using descriptive statistics (e.g., means and standard deviations, frequency and percent). Within group differences for laboratory outcomes at each dose will be evaluated for significance using paired t tests. Data will also be presented visually using histograms and line graphs. Treatment-emergent AEs will be organized by body system and summarized in table format by dose, with AE severity and possible relation to study drug reported.

L.3. Feasibility analysis (Aim 3)

The feasibility of administering REDCap surveys will be assessed by calculating the percentage of administered questionnaires that are returned and fully completed by participants, with feasibility defined as at least 80% of all administered questionnaires returned and completed. For each of the four timepoints (prior to PK Visit 1 and 2, prior to 4-Week Follow-Up Visit 1 and 2), the percentage of administered questionnaires returned and the percentage of returned questionnaires that are fully completed will also be reported.

L.4. Sample size

Based on a paired sample t-test with $\alpha=0.05$ and a sample size of 10 (anticipating two dropouts), we will have 95% power to detect an effect size of 1.3 (Cohen's d). Based on plasma levels of withaferin A, withanoside IV, and withanolide A observed in an unpublished PK study of 480 mg Shoden® in 16 healthy adults,⁷⁹ this effect size would be a difference in C_{\max} between the two doses of about 6.5 ng/ml for withaferin A, 2.2 ng/ml for withanoside IV, and 1.17 ng/ml for withanolide A. We expect to see much bigger differences between the two doses based on previous botanical studies where half doses resulted in C_{\max} values that were 35-50% lower than the full dose.⁸¹⁻⁸⁴

L.5. Data quality and management

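### L.2 tests laboratory change only before versus after within each dose, so a red-cell fall caused by about 195 mL of study blood sampling can be mistaken for a Shoden effect

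*Combined protocol and SAP*

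**What the plan says.** **Analysis.** L.2 (Safety analysis, Aim 2) first describes the data: "Changes in laboratory outcomes from the baseline visit to the four-week follow-up visit for each study period will be presented using descriptive statistics". It then gives the only inferential step for laboratory values: "Within group differences for laboratory outcomes at each dose will be evaluated for significance using paired t tests". Histograms, line graphs and an adverse-event table by dose complete the section. No laboratory comparison between 480 and 240 mg is stated, and blood loss is not mentioned. L.1 sets the testing convention: "All final statistical tests will be two-tailed and considered significant at" 0.05.

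**Design.** F.1 describes a two-period randomized crossover of two active doses with the same pharmacokinetic sampling in each period. There is no placebo or untreated period. L.1 compares the doses within participant for the pharmacokinetic parameters.

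**Sampling.** At the baseline visit (I.4.1), "a baseline plasma sample of two teaspoons (10 ml) will be collected through the catheter" before dosing, followed by 14 post-dose samples of the same size, 20 mL for safety labs including the CBC, and 5 mL for a repeat CMP. The section gives the total: "This visit is expected to take 13 hours a total of 175 mL of blood will be collected". I.4.2 adds: "Participants will return at 24 hours and 48 hours for a single blood collection (two teaspoons (10 ml)) and urine collection". The 48-hour visit may be dropped if nothing is detected in the first two participants. The second CBC of the period is taken at the four-week follow-up visit.

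**Size.** F.2.1 states: "We expect two dropouts, for a total of 10 participants completing the study".

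**The concern.** A before-after change in an uncontrolled period is the sum of everything that happened in that period. Here one of those things is known in advance, acts in one direction on red-cell measures, and comes from the protocol itself. The baseline CBC is drawn at the start of the visit (a low result halts it), before most of the blood is taken. The four-week CBC comes after all of it. If the red-cell mass is not fully restored by then, hemoglobin, hematocrit and red-cell count fall on average at both doses even if Shoden does nothing.

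Aim 2 concerns the safety of both doses, and the only experience with 480 mg that the protocol cites is a single administration in 16 participants. A significant p-value for hemoglobin under the safety heading, with no caveat, invites a wrong reading. The randomized within-person dose contrast, in which equal blood loss cancels, is available but not planned for laboratory outcomes.

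**Working it through.** **1. The plan's own figures.**

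- Baseline visit: 10 (pre-dose) + 14 × 10 (post-dose) + 20 (safety labs) + 5 (10-hour CMP) = 175 mL. This matches the stated total.
- Through 48 hours: 175 + 2 × 10 = 195 mL. Without the 48-hour visit: 185 mL. The 20 mL safety draw is counted because that blood leaves the body as the baseline CBC is taken; leaving it out gives 175 mL.
- L.4 states "we will have 95% power to detect an effect size of 1.3" with 10 participants and a paired t-test. Two-sided noncentral t, df = 9, noncentrality 1.3 × √10 = 4.11, gives 95.4%. The stated figure reproduces, so the same method is used below.

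**2. Size of the sampling effect.** These inputs are assumptions, not in the documents: blood volume 4.5–5.0 L and starting hemoglobin 13.5 g/dL.

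Fall before recovery = hemoglobin × volume drawn ÷ blood volume:

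- 5.0 L: 195/5000 = 3.9%; 13.5 × 0.039 = 0.53 g/dL
- 4.5 L: 195/4500 = 4.3%; 13.5 × 0.0433 = 0.585 g/dL

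I use 0.55 g/dL for no recovery, 0.27 for half, 0.14 for three quarters and 0 for full recovery by week 4. With wider assumptions (4.0–5.5 L, hemoglobin 12.5–14 g/dL) the unrecovered fall is 0.44–0.68 g/dL.

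**3. Chance that one within-dose test is significant with no product effect.** n = 10, two-sided 0.05, df = 9, noncentrality = (residual fall ÷ SD of change) × √10. The SD of change, 0.4–0.6 g/dL, is assumed.

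| Recovery by week 4 | Residual fall (g/dL) | Noncentrality, SD 0.6 to 0.4 | Chance of p < 0.05 |
|---|---|---|---|
| Full | 0 | 0 | 5% |
| 75% | 0.14 | 0.74 to 1.11 | 10–17% |
| Half | 0.27 | 1.42 to 2.13 | 25–48% |
| None | 0.55 | 2.90 to 4.35 | 73–97% |

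**4. The dose contrast.** If the same volume is drawn in both periods, the expected sampling effect in the 480-minus-240 mg difference in change is zero. Period 2 may start from a hemoglobin still recovering from period 1, which is a period effect and is why the contrast should be adjusted for period.

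Precision, assuming changes independent between periods: SD of the difference = √2 × SD of change = 0.57 to 0.85 g/dL. At n = 10 with period in the model (df = 8, balanced sequences), 80% power needs a standardized difference of about 1.01. The detectable difference is therefore 1.01 × 0.57 = 0.57 to 1.01 × 0.85 = 0.86 g/dL, as large as or larger than the whole unrecovered fall of 0.55 g/dL.

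**The case against.** A reader might infer that a phlebotomy fall will be reported as a Shoden effect. The documents do not support that. L.2 says which test is run, not that a significant change is attributed to the product. Section N has abnormal individual results examined for causes, and N.1 weighs alternative explanations before an adverse event is attributed. Those rules act on individuals and do not govern a mean shift tested under L.2, so the risk of misreading remains, but it is a risk and not a certainty.

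A reader might also infer that laboratory safety rests on these tests alone. It does not: L.2 also plans descriptive summaries, graphs and adverse events by dose. None of these separates blood loss from product effect.

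Three further points stand:

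- The probabilities rest on recovery, SD, blood volume and hemoglobin values that the documents do not give, and they run from the nominal 5% to 97%. Material distortion is possible, not shown.
- The mechanism concerns red-cell indices. The protocol's named laboratory concerns are liver, renal, thyroid and testosterone, and no bias is shown there.
- Cancellation in the dose contrast is approximate. A visit halted for difficult sampling can leave a participant in the study with less blood drawn in that period, and dropping the 48-hour draw could leave the early participants with unequal volumes in their two periods.

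The strongest objection is to relying on the contrast. Aim 2's hypothesis concerns tolerability at each dose, and an effect common to both doses vanishes from a dose difference. That rules out replacing the within-dose results, but it does not argue against adding the contrast.

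**Conclusion.** The point holds for red-cell indices. The plan's own volumes place 195 mL of sampling per period (185 mL without the 48-hour visit) between the two blood counts, and the only planned laboratory test cannot separate that loss from a product effect. The chance of a significant hemoglobin change from phlebotomy alone is 5% with full recovery by week 4, 10–17% with 75%, 25–48% with half and 73–97% with none. These figures are for one dose and one test, with 10 completers and an assumed SD of change of 0.4–0.6 g/dL.

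For the other laboratory outcomes the gap is narrower: no between-dose comparison is planned although the crossover provides one. Nothing here shows that liver, renal, TSH or testosterone results are biased by sampling. This is worth correcting before analysis, because the correction prevents a confounded conclusion and needs no new data.

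**What to change.** In L.2:

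1. Keep the within-dose baseline-to-four-week changes.
2. Add, for each laboratory outcome, the within-participant 480-minus-240 mg difference in that change, adjusted for period, with a 95% CI.
3. State that within-dose changes in hemoglobin, hematocrit and red-cell count include about 195 mL of study phlebotomy (185 mL if the 48-hour visit is dropped) and will not be attributed to Shoden on the within-dose test alone.
4. State that a dose contrast near zero is not evidence of safety, because it cannot show an effect common to both doses.

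The cost is wording and a modest amount of analysis on data already collected. The limitation is precision: under the assumptions above, the contrast has 80% power only for hemoglobin differences of about 0.6–0.9 g/dL. It should be reported as an interval alongside the within-dose results, not in their place.
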